8 STUDY ASSESSMENTS AND PROCEDURES

8.1 EFFICACY ASSESSMENTS

We will capture all survey data via REDCap. REDCap is a secure web application for building and managing online surveys and databases. While REDCap can be used to collect virtually any type of data (including 21 CFR Part 11, FISMA, and HIPAA-compliant environments), it is specifically geared to support online or offline data capture for research studies and operations. If subjects do not complete the surveys, they will be sent a reminder prompt.

Primary Outcome

The change from study baseline to Week 8 in monthly pain intensity as measured by the standard 11-point numeric rating scale (NRS) scale is the primary endpoint. Consistent with NIH Helping to End Addiction Long- Term (HEAL) guidance, we will measure daily pain with NRS for 7-days during baseline week 0, and again during the final week of the study (week 8). The minimally clinically importance difference (MCID) on the pain NRS is 2 points.

Secondary Outcomes

The change from study baseline to week 8 in pain interference as measured by the 8-item PROMIS PI scale is a secondary endpoint. The scale is rendered using a T-statistic, where a score of 50 represents the population mean and 10 points is a standard deviation (SD). Scoring of the instrument will occur in a SAS/R/STATA environment in which study statisticians are blinded to the study arm.

The change from baseline to Week 8 in pain catastrophizing as measured by the 4-item short pain catastrophizing scale is a secondary endpoint. The Pain Catastrophizing scale (PCS) short form measures rates of high catastrophizing as defined by a score of ≥ 7 . Scoring of the instrument will occur in a SAS/R/STATA environment in which study statisticians are blinded to the study arm.

The change from study baseline to Week 8 in anxiety as measured by the PROMIS Anxiety Scale is a secondary endpoint. The scale is rendered using a T-statistic, where a score of 50 represents the

population mean and 10 points is a standard deviation (SD). Scoring of the instrument will occur in a SAS/R/STATA environment in which study statisticians are blinded to the study arm.

The change from study baseline to week 8 in pain interference as measured by the 8-item PROMIS Pain Interference scale is a secondary endpoint. The pain interference scale measures the consequences of pain on relevant aspects of one's life. This includes the extent to which pain hinders engagement with social, cognitive, emotional, physical, and recreational activities. The scale is rendered using a T-statistic, where a score of 50 represents the population mean, and 10 points is a standard deviation (SD).

The change from study baseline to week 8 in pain self-efficacy as measured by the two-item Pain Self-Efficacy Questionnaire (PSEQ-2) is a secondary endpoint. It is a two-item instrument designed to assess the extent to which people in pain believe they are presently able to work and live a normal life despite pain (work includes housework and paid and unpaid work). There is strong evidence for the validity and reliability of the PSEQ-2, its sensitivity to change, and suitability in clinical and research settings.

The change from baseline to Week 8 in 7-day average of daily maximum milligrams morphine equivalent (MME). Prescription opioid medication use will be collected via self-report and calculation of the 7-day average will occur in a SAS/R/STATA environment in which study statisticians are blinded to the study arm.

8.2 SAFETY AND OTHER PROCEDURES

Safety will be monitored by following up with participants for any adverse events (AE), assessment of adherence, monitoring of biometric information, and questionnaires by support staff.

8.2.1 PROCEDURES

Virtual Reality Headset data

Data from the PICO G2 4K device will be aggregated by AppliedVR's cloud-based software solution that implements robust industry standards to maintain secure databases and keep data private. The AppliedVR cloud server is a HIPAA compliant platform. The device account that corresponds with each device will be created using a clinical trial number that is only linked to the patient via our office list of patients enrolled in the study. AppliedVR does not collect personally identifiable information and does not collect IP addresses from synced participant devices in our database. Data will be stored and indexed in the AppliedVR server database whenever devices upload batches of analytic events, and the analytic events are timestamped. The data collected by the device will include time of use, date of use, and the module selected. Our database servers are IP firewalled and whitelisted such that they refuse any connection from IP addresses not preprogrammed by our team.

PAINTRAINER

PainTRAINER® metadata will be downloaded and provided monthly by the coordinator at Northwestern as CSV files containing timestamped records of content accessed at the individual device level. These records will feature a user-ID unique to each patient. A linking list containing study-IDs and user-IDs will be stored on a secure server behind the Cedars-Sinai firewall, and only associated with other study data following database lock. In order to monitor weekly adherence, study-staff will access a subset of the metadata limited to study-ID and timestamps of usage. These data will be subjected to QC procedures in a SAS/STATA/R environment.

Technical Support

Patients in both arms will receive remote technical support from the research team. The idea is that issuing technology is usually insufficient to achieve behavior change.

Patients will be provided with onboarding material as well as emails with a link to our lab's website. The website was developed based on experience from previous remote VR therapy clinical trial and feedback from patients within it. On the website we have instructional videos as well an extensive FAQ page.

REDCap survey data will also be monitored. We will assign two technical support staff members to monitor patients in both arms. Patients will receive a telephone number and email to contact support staff as needed.

8.3 ADVERSE EVENTS AND SERIOUS ADVERSE EVENTS

8.3.1 DEFINITION OF ADVERSE EVENTS (AE)

An adverse event (AE) is defined as any untoward medical occurrence associated with the use of an intervention in humans, whether or not considered intervention-related (21 CFR 312.32 (a)). Short-term AEs associated with the study include "cybersickness,"³² a transient form of motion sickness that affects up to one in four people upon entering a VR environment. Cybersickness most commonly presents with a short-term feeling of dizziness that typically subsides quickly. There are no anticipated long-term AEs from participating in this study. A comprehensive list of all potential cybersickness symptoms can be found below:

- Nausea
- Fatigue
- Eyestrain
- Blurred vision
- Difficulty focusing
- Dizziness
- Vertigo (a sensation of spinning dizziness, as though the room or surrounding environment is spinning)
- Headache
- Fullness of the head
- Difficulty concentrating
- Postural instability

In very rare instances, materials used in VR headsets have caused a mild rash which resolves when the VR headset is discontinued. Participants may also experience neck pain if using the device. No AEs are expected with PainTRAINER.

8.3.2 DEFINITION OF SERIOUS ADVERSE EVENTS (SAE)

A serious adverse event (SAE) or suspected adverse reaction is considered "serious" if, in the view of either the investigator or sponsor, it results in any of the following outcomes: death, a life-threatening adverse event, inpatient hospitalization or prolongation of existing hospitalization, a persistent or significant incapacity or substantial disruption of the ability to conduct normal life functions. Important medical events that may not result in death, be life-threatening, or require hospitalization may be

considered serious when, based upon appropriate medical judgment, they may jeopardize the participant and may require medical or surgical intervention to prevent one of the outcomes listed in this definition. We do not expect any serious adverse events with the EaseVRx or PainTRAINER intervention.

8.3.3 CLASSIFICATION OF AN ADVERSE EVENT

8.3.3.1 SEVERITY OF EVENT

For adverse events (AEs) the following guidelines will be used to describe severity.

- **Mild** – Events require minimal or no treatment and do not interfere with the participant's daily activities.
- **Moderate** – Events result in a low level of inconvenience or concern with the therapeutic measures. Moderate events may cause some interference with functioning.
- **Severe** – Events interrupt a participant's usual daily activity and may require systemic drug therapy or other treatment. Severe events are usually potentially life-threatening or incapacitating. Of note, the term "severe" does not necessarily equate to "serious".

Research staff will call the patient if an event is noted in event assessment that is sent on a biweekly basis. Nothing more than mild to moderate side effects are expected.

8.3.3.2 RELATIONSHIP TO STUDY INTERVENTION

All adverse events (AEs) must have their relationship to study intervention assessed by the clinician who examines and evaluates the participant based on temporal relationship and his/her clinical judgment. The degree of certainty about causality will be graded using the categories below. In a clinical trial, the study product must always be suspect.

- **Related** – The AE is known to occur with the study intervention, there is a reasonable possibility that the study intervention caused the AE, or there is a temporal relationship between the study intervention and event. Reasonable possibility means that there is evidence to suggest a causal relationship between the study intervention and the AE.
- **Not Related** – There is not a reasonable possibility that the administration of the study intervention caused the event, there is no temporal relationship between the study intervention and event onset, or an alternate etiology has been established.

8.3.3.3 EXPECTEDNESS

Research staff will be responsible for determining whether an adverse event (AE) is expected or unexpected. An AE will be considered unexpected if the nature, severity, or frequency of the event is not consistent with the risk information previously described for the study intervention.

8.3.4 TIME PERIOD AND FREQUENCY FOR EVENT ASSESSMENT AND FOLLOW-UP

The occurrence of an adverse event (AE) or serious adverse event (SAE) may come to the attention of study personnel during review of biweekly event assessments by a study team member as well as on

Day 1. We will employ a general question to allow the patient to provide an event description without bias by presupposing the nature of the event, as follows:

- 1) During the past 14 days, have you experienced anything uncomfortable, distressing or upsetting as a result of using the technology?
 - a. Yes
 - b. No
- 2) If Yes please describe what happened. A research staff member will follow-up with you as soon as possible to learn more.
 - a. [open text]

A designated CRC will review the REDCap dashboard for completed AE assessments on a daily basis throughout the work week. Once they find a completed event assessment form, they will follow-up with a phone call. The following information be obtained from the patient during the call: onset of potential adverse event, event description, when they last used the technology, how long they used the headset, when they stopped using the headset, severity of the potential AE, outcome of the potential AE (see categories, below), time until resolution/stabilization of event, the perceived relationship of the event to the study intervention, whether or not the event was expected (Y/N), whether it was serious.

The outcome can be labeled using one of the following categories:

- Recovered, without treatment
- Recovered, with treatment
- Still Present, no treatment
- Still Present, being treated
- Residual effect(s) present-no treatment
- Residual effect(s) present-being treated

Research staff will record all reportable events with start dates occurring any time after informed consent is obtained until 7 (for non-serious AEs) or 30 days (for SAEs) after the last day of study participation.

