1 PROTOCOL SUMMARY

1.1 SYNOPSIS

Title: Transcending COVID-19 barriers to pain care in rural America: Pragmatic comparative effectiveness trial of evidence-based, on-demand, digital behavioral treatments for chronic pain

Study Description: This study will compare two available, evidence-based, digital pain treatment programs that patients can use at home. The goal is to see if one approach is better than the other, and whether certain patients respond to one more than the other. Study participants will be randomized to receive one of two treatment programs: Skills-Based VR or PainTRAINER. Study devices will be delivered to the participant's home with instructions for use via FedEx; participants will receive remote technical support. They will be followed for 8 weeks and complete Patient Reported Outcome (PRO) questionnaires to assess functional status, pain levels, and use of pain medications (including opioids). Participants will also be asked to provide consent/authorization to access medical records from their treating facility.

[figure not shown]
Objectives: Primary Objective:
To compare the effectiveness of EaseVRx and PainTRAINER in improving perceived pain intensity from baseline to 8 weeks.

Secondary Objectives:

- To compare the effectiveness of EaseVRx and PainTRAINER in improving perceived pain catastrophizing over 8 weeks.
- To compare the effectiveness of EaseVRx and PainTRAINER in improving PROMIS anxiety over 8 weeks.
- To compare the effectiveness of EaseVRx and PainTRAINER in improving PROMIS pain interference over 8 weeks.
- To compare the effectiveness of EaseVRx and PainTRAINER in improving pain self-efficacy over 8 weeks.
- To compare the effectiveness of EaseVRx and PainTRAINER in reducing use of opioids over 8 weeks.

Endpoints:	Primary Endpoint: Daily Pain Intensity Secondary Endpoints: PROMIS Pain Interference, PROMIS Anxiety, Pain Catastrophizing, Pain Self-efficacy, and MME usage.
Study Population:	Individuals over age 13 with an ongoing pain problem that have experienced average pain intensity of >3 out of 10 within the previous 7 days.
Phase:	Phase 2
Description of Sites/Facilities Enrolling Participants:	Four outpatient clinic sites, including Cedars-Sinai Medical Center; Ochsner Medical Center; The University of Alabama at Birmingham; Bendcare Physician Network. In addition, participants may enroll remotely.

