7.3 LOST TO FOLLOW-UP

A participant will be considered lost to follow-up if he or she fails to schedule an onboarding phone call within 30 days of device delivery or if he or she fails to complete the initial SSQ+ survey within 30 days of onboarding completion. For participants who complete the initial SSQ+ survey and fail to complete >80% of future surveys, and become unreachable by phone or email, the participant will be considered lost to follow-up 6 days following the email date of the participant's Day 60 survey.

If a participant fails to complete the weekly surveys within six days, the following actions will be taken:

- The research coordinator will attempt to contact the participant and counsel them on the importance of completing surveys and returning the equipment to be eligible for the gift card.
- Before a participant is deemed lost to follow-up, the investigator or designee will make every effort to regain contact with the participant (where possible, 3 telephone calls and, if necessary, a certified letter to the participant's last known mailing address or local equivalent methods). Contact attempts will be documented in the participant's study record.
- Should the participant continue to be unreachable, he or she will be considered to have withdrawn from the study with a primary reason of lost to follow-up.

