10.1.8 DATA HANDLING AND RECORD KEEPING

10.1.8.1 DATA COLLECTION AND MANAGEMENT RESPONSIBILITIES

Study staff will develop, test, and maintain the data capture system using a web-based data collection system, REDCap, as the primary source of data entry and storage. Developed by Vanderbilt University, REDCap is a software toolset and workflow methodology for electronic collection and management of research and clinical trial data. The REDCap system provides a secure, web-based application that is flexible and provides: 1) an intuitive interface for users to enter data and have real time validation rules (with automated data type and range checks) at the time of entry; 2) HIPAA compliant audit trails for tracking page views, data manipulation and export procedures; 3) record locking and electronic signature functions; 4) control over user rights to view and manipulate data; 5) a report builder capable of querying patient records; and 6) automated export procedures for SAS/R/STATA datasets.

The REDCap system complies with all applicable guidelines to ensure patient confidentiality, data integrity, and reliability. Quality assurance and control procedures will be applied to ensure the completeness, validity, and accuracy of the study database. The MOOP describes data collection processes, database development procedures, quality control processes, and reporting in greater detail.

EHR data will be retrieved by the Research Informatics and Scientific Computing Core (RISCC) at Cedars-Sinai, which facilitates interaction between the research community and the Epic data warehouse and production environment. We will collaborate with RISCC to design queries for portions of participants' records as defined in the data dictionary. The data extracts issuing from these queries will be delivered monthly as CSV files via Box and/or OneDrive, HIPAA-compliant cloud content management systems. These will then be converted to SAS/R/STATA data sets and subjected to QC procedures in a SAS/R/STATA environment.

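### Section 8.3.4 relies mainly on a participant-completed form to find serious events and has no label for death, so SAEs can be under-counted, above all in participants closed as lost to follow-up

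*Combined protocol and SAP*

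**What the plan says.** - **Finding events (8.3.4).** An AE or SAE "may come to the attention of study personnel during review of biweekly event assessments", and also on Day 1. The form looks back 14 days and asks: "have you experienced anything uncomfortable, distressing or upsetting as a result of using the technology". Next comes the call: "Once they find a completed event assessment form, they will follow-up with a phone call". Event details are "obtained from the patient during the call". Section 8.3.3.1 ties the call to an event being noted on the form.
- **Outcome labels (8.3.4).** There are six: two for recovery, two for an event still present and two for residual effects. By contrast, the serious outcomes in 8.3.2 begin with "death, a life-threatening adverse event, inpatient hospitalization or prolongation of existing hospitalization".
- **Recording window (8.3.4).** SAEs are to be recorded from consent until 30 days after the last day of participation.
- **Non-response (6.4, 7.3).** Missed surveys are expected and are not non-compliance. Reminders are followed by a call. Before closure, 7.3 provides for three calls where possible and a certified letter if needed. If contact still fails, "he or she will be considered to have withdrawn from the study with a primary reason of lost to follow-up".
- **Records (1.1, 10.1.8.1).** "Participants will also be asked to provide consent/authorization to access medical records from their treating facility". For the EHR queries run by the Cedars-Sinai informatics core, "The data extracts issuing from these queries will be delivered monthly as CSV files". No section uses either source to find SAEs or deaths.
- **Analysis and oversight (9.3, 9.4.4, 10.1.5, 10.1.6).** Safety is summarised by arm in all randomised participants, descriptively only. There is no DSMB; the reviewing IRB looks at safety data once a year.

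**The concern.** A participant who has died cannot return a form, and one in hospital may be unable to. A missing form does not start the safety call and, under 6.4, is not an alarm. If the retention contacts also fail, the file is closed as a withdrawal and nothing records that a serious event took place. Even when staff do learn of a death, the outcome list has nowhere to put it.

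At stake is the by-arm safety summary and what the IRB sees at its yearly review. Participants with no recorded event remain in the denominator, so silence reads as absence of harm. If drop-out differs between arms, the shortfall can differ as well. A report of no serious events would then rest mainly on the people able to answer, and on the events they attributed to the technology.

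**Working it through.** The plan gives no expected SAE rate and no expected drop-out rate, so it has no figure of its own to reproduce. The check is mainly a comparison of sections.

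**Step 1. Instrument against requirement.**

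| Requirement | What the form and call provide |
|---|---|
| Death is an SAE outcome (8.3.2) | No fatal label among the six, and none for unknown |
| Hospital stays count as SAEs, whether or not related to the intervention (8.3.1, 8.3.2) | Question limited to events resulting from the technology |
| All randomised participants are in the safety summary (9.3) | Call follows a completed form; details come from the patient |
| Recording from consent to 30 days after participation (8.3.4) | Events Assessment marked in Weeks 1 to 9 only (1.3, as extracted) |

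**Step 2. Stretch without a form.** Count Week 9 as ending on day 9 × 7 = 63.
- Participation ending at Week 8 (completion as defined in 4.4): 56 + 30 = day 86, and 86 − 63 = 23 days without a form.
- Participation ending at Week 12 (duration in the synopsis): 84 + 30 = day 114, and 114 − 63 = 51 days without a form.

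The window also opens at consent, while the first form is in Week 1. The schedule was read from a PDF table, so its column positions should be confirmed. Separately, 8.3.4 calls the form biweekly and the schedule marks it every week.

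**Step 3. Illustrative size.** N = 300 (5.5). Every rate below is an assumption.
- Route A: 300 × share with an SAE (2% to 5%) × share of those who stop answering (25% to 50%). Low: 6 × 0.25 = 1.5. High: 15 × 0.50 = 7.5.
- Route B: 300 × share who stop answering (5% to 30%) × SAE risk in the window (1% to 10%). Low: 15 × 0.01 = 0.15. High: 90 × 0.10 = 9.
- One point within route B: 300 × 0.10 × 0.03 = 0.9 expected events. The chance of at least one is 1 − 0.97^30 = 0.60.

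These are SAEs falling among people who stop answering. Those learned of through calls, the letter or relatives would not be missed. The ranges leave out unrelated or late SAEs missed in people who do answer; the documents give no basis for sizing those.

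**The case against.** A reader might infer that forms are the only route by which a serious event can be found. The documents do not say so. Section 8.3.4 uses permissive wording, and 8.2 adds follow-up with participants, adherence and biometric monitoring. Section 8.2.1 gives both arms a support line. Section 6.4 has a call that asks why reminders were missed, 7.3 has calls and a letter, 5.5 allows portal contact by the recruiting site, and 7.2 requires the reason for withdrawal. The reporting clock in 8.3.6 runs from awareness, however gained. A relative answering the telephone would be enough. The under-count is therefore possible, not certain. What stands is that the contacts in 6.4 and 7.3 are written for survey completion and equipment return, that none is told to ask about death or admission, and that closure needs no record check.

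A reader might also work out how far the upper limit on the VR arm's SAE rate could move. The one-sided exact 95% limit is 2.0% for 0 of 150, 5.1% for 3 of 150 and 6.0% for 4 of 150. The documents do not support that use. An even split of route A's 1.5 to 7.5 gives 0.75 to 3.75 per arm, so 3 missed events is near the top and 4 is beyond it. The comparison also needs none to have been seen. If 25% to 50% of those affected stop answering, the chance that all of three do so is 0.25³ = 1.6% to 0.5³ = 12.5%.

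The EHR extract could likewise be read as a ready and complete remedy. It is described only for the Cedars-Sinai core. Section 5.5 expects more participants from Alabama and Louisiana than from California, and says the target population is unlikely to live near the participating systems. Extract contents are left to a data dictionary that is not among the documents, so admissions may already be included.

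Finally, this is described as a minimal-risk study and safety is not tested. That limits the weight of the point but does not remove the coding gap or the missing check.

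**Conclusion.** The point holds in a limited form. The absence of a label for death conflicts with 8.3.2 and needs no assumption. It also follows from the text that, by default, an unreachable participant is closed without a check of vital status or admission and still counts in the safety denominator. That an unrelated or late SAE can be missed in a full responder follows from the question's wording and from the schedule as extracted.

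The size of the under-count cannot be derived from the documents. Under the assumed rates it runs from under 1 to about 8 or 9 events in 300, taking every SAE in a non-responder as missed. The effect is on descriptive safety reporting and on recorded reasons for loss to follow-up; the primary test is untouched. The change is worth making because it is cheap, not because a large bias has been shown.

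**What to change.** 1. Add *Fatal* and *Unknown* to the outcome list in 8.3.4.
2. In 7.3, before coding a participant lost to follow-up, check the medical records for which authorisation was given for death or hospital admission, from consent to 30 days after last participation. Use the Cedars-Sinai extract where it applies and a look-up by the recruiting site otherwise. Where closure comes before those 30 days have run, repeat the check once they have.
3. Pass any hit to the seriousness and relatedness assessments in 8.3.2 and 8.3.3.2. Do not enter it automatically as an SAE: a planned admission, for example, needs that judgement.
4. Report by arm the number of randomised participants with unknown vital status.

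These steps do not reach full responders. The form's question, its timing in 1.3 (weekly or biweekly, and the last form) and the recording window in 8.3.4 must therefore also be reconciled.

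Cost: two labels, a short addition to the protocol and one line in the disposition table, plus record look-ups for participants outside the Cedars-Sinai extract, who may be the majority. Care outside the participating systems will still be missed, which is why item 4 is needed.

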1.2 SCHEMA

1.3 SCHEDULE OF ACTIVITIES (SOA)

Procedures	Baseline / Screening	Day 1 of Week 1	8-Week Intervention									Post Intervention
	0	1	1	2	3	4	5	6	7	8	9	
Week	0	1	1	2	3	4	5	6	7	8	9	12
Prospective patients identified (Cohort Builder or Provider)	X											
Informed consent in person or over phone	X											
Verify eligibility in chart review or from [name]:	X											
• Medical history												
• Demographics												
Randomization	X											
Baseline Questionnaires (Listed below with)	X											
Shipment of VR device and/or study documents	X											
Technical onboarding call		X										
Milligram Morphine Equivalent (MME) Daily Dose	X										X	
Return of VR Device												X
Deliver honorarium						X					X	X
Self-Reported Questionnaires												
NIH developed baseline demographics, biological sex	X (Day 1)											
Daily Pain Medications Used	X										X	
Daily Pain Intensity	X										X	
Pain Catastrophizing Scale	X (Day 4)		X	X	X	X	X	X	X	X	X	
PROMIS Anxiety Scale	X (Day 4)		X	X	X	X	X	X	X	X	X	
PROMIS Pain Interference Scale	X (Day 4)		X	X	X	X	X	X	X	X	X	
The Pain Self-Efficacy Questionnaire (PSEQ) 2-item short form	X (Day 4)		X	X	X	X	X	X	X	X	X	
Simulator Sickness Questionnaire (VR Only)		X										
Treatment Usage Questionnaire			X	X	X	X	X	X	X	X	X	X
Events Assessment			X	X	X	X	X	X	X	X	X	
Custom Questions		X									X	
Treatment Expectation	X (Day 4)	X										
Concomitant Procedures Questionnaire	X (Day 4)										X	
Primary Pain Questionnaire											X	
Coping with Weekly Pain Questionnaire	X (Day 7)										X	X

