6.1.2 DOSING AND ADMINISTRATION

All participants are instructed to use the VR program at least once a day and as needed throughout the 8 week study period. Thereafter, the participant can use the program as needed. Section 4.3 provides the justification of dose. PainTRAINER delivers eight sessions via any web-connected platform,

including Android or iOS smartphones, tablets, or personal computers. Patients will complete one session per week in a pre-determined order.

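### The event form is weekly in the schedule but biweekly in the text, with a 14-day recall, and no form is scheduled after Week 9 although the synopsis gives 12 weeks of participation

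*Combined protocol and SAP*

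**What the plan says.** The event question in section 8.3.4 has a fixed recall: "During the past 14 days, have you experienced anything uncomfortable, distressing or upsetting as a result of using the technology".

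The documents give its frequency in two ways.

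- **Text.** Section 8.3.3.1 says "Research staff will call the patient if an event is noted in event assessment that is sent on a biweekly basis". Section 8.3.4 says events may come to light "during review of biweekly event assessments by a study team member as well as on" Day 1.
- **Schedule.** The header in section 1.3 reads "Week 0 1 1 2 3 4 5 6 7 8 9 12" and the event row reads "Events Assessment X X X X X X X X X". The nine marks sit under Weeks 1 to 9. Week 0, Day 1 and Week 12 are blank.

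Section 8.3.4 says staff record events "until 7 (for non-serious AEs) or 30 days (for SAEs) after the last day of study participation". On use after the eight-week programme, section 6.1.2 says "Thereafter, the participant can use the program as needed". The schedule marks the Treatment Usage Questionnaire at Week 12.

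The length of participation is also given in two ways. The synopsis gives a participant duration of 12 weeks, section 5.5 speaks of retention to a 12-week study, and section 6.4 pays for three months of follow-up. The synopsis's study description gives 8 weeks of follow-up, and section 4.4 defines completion by the Week 8 survey. Headset return is tied to the Week 8 surveys in section 5.5 and marked at Week 12 in the schedule.

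**The concern.** Staff cannot follow both frequencies. A 14-day recall fits a form sent every 14 days. Sent weekly, the same question asks about most days twice, so one episode can produce two positive forms and two follow-up calls. The plan states no rule for recognising or counting repeats, and section 9.4.4 says only that safety analyses are descriptive.

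The second problem does not depend on frequency. The scheduled forms stop at Week 9, but the stated recording window runs past the end of participation. At Week 12 the trial asks whether the programme is still being used but does not ask about harm. Late events are then captured only if participants volunteer them, while earlier events are asked about. What is at stake is how far the safety summary can be read as complete. The primary efficacy result is not affected.

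**Working it through.** The plan states no figure to reproduce, so the check counts how many scheduled forms cover each day.

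**Inputs.** Recall is 14 days (8.3.4). Forms are weekly in Weeks 1 to 9 (1.3) or every 14 days (8.3.3.1 and 8.3.4). Participation is 12 weeks = 84 days (synopsis) or 8 weeks = 56 days (study description and 4.4). The day within the week on which a form is answered is not given. Week end is assumed, with week start as a sensitivity case.

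**Rule.** A form answered on day f covers days f − 13 to f.

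**Weekly forms at week end** (days 7, 14, ..., 63). Days 1 to 56 each lie in two forms, days 57 to 63 in one, and days 64 to 84 in none. As a check, 9 × 14 = 126 form-days, less the 7 that fall before Day 1, is 119 = 2 × 56 + 7.

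| Schedule, answered on time | Covered twice | Uncovered of 84 |
|---|---|---|
| Weekly, week end | 56/63 = 88.9% of covered days (56/84 = 66.7% of all) | 84 − 63 = 21 (25.0%) |
| Weekly, week start (days 1, 8, ..., 57) | 50/57 = 87.7% of covered days | 84 − 57 = 27 (32.1%) |
| Biweekly, end of Weeks 1, 3, 5, 7, 9 | 0 | 21 (25.0%) |
| Biweekly, end of Weeks 2, 4, 6, 8 | 0 | 84 − 56 = 28 (33.3%) |

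**Recording window.** If participation ends at Day 84, the window closes at Day 84 + 7 = 91 for non-serious events and Day 84 + 30 = 114 for serious ones. If it ends at Day 56, the window closes at Day 63 or Day 86. A form at the end of Week 9 (Day 63) then covers all of participation and the 7-day window, and leaves 86 − 63 = 23 days of the serious-event window. If the last biweekly form is at Day 56, the 7-day window is not covered either.

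**Late completion.** Section 6.4 lets surveys be answered out of order and on the same day. Suppose biweekly forms fall due on Days 14 and 28, and the first is answered 7 days late, on Day 21. The first covers days 8 to 21 and the second days 15 to 28. Days 15 to 21 are then asked about twice and days 1 to 7 not at all. So correcting the frequency alone does not remove overlap or gaps. Lateness can also narrow the end gap: with weekly forms, a Week 9 form answered 14 days late (Day 77) leaves 14/84 = 16.7% uncovered.

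**The case against.** A reader might infer that events will be double-counted in the safety summary. The documents do not support that. The overlap arises only if the schedule row is followed, and the biweekly text removes it when forms are on time. Nothing says positive forms are what is counted. A form triggers a call, and the call collects the onset date, so a repeat can be recognised. What stands is the contradiction on frequency and the lack of a stated counting rule.

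A reader might also infer that late events go uncaptured. That is too strong. Section 8.3.4 still requires recording after participation, section 8.2 provides for following up participants for adverse events, and section 8.2.1 gives them a support telephone number and email. What stands is that no scheduled question prompts a late report.

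The 25% depends on 12 weeks of participation, and the 8-week passages are real. With an 8-week end and a Week 9 form, no day of participation is uncovered. The 12-week reading nevertheless has the synopsis's participant duration, the retention text, the month-3 payment and the Week 12 survey behind it. How long headset users could continue is itself contradictory.

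Three further inferences should not be drawn:

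- The Week 1 recall reaches back before first use, but the question is limited to effects of the technology, so this cannot generate qualifying events.
- The schedule leaves the event row blank at Day 1, and its simulator sickness questionnaire is for the VR arm only. But Custom Questions are marked that day, and section 6.4 names an SSQ+ survey. Their content is not shown, so a missing Day 1 event question cannot be established.
- Section 10.1.2 mentions assessments at 14-day intervals but does not name event forms, so it does not settle the frequency.

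Finally, the main expected event is transient cybersickness on entering VR, which makes late harm less likely. That limits the weight of the point but does not remove the gap.

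**Conclusion.** The point holds in two parts. First, the schedule and the text contradict each other on event-form frequency. Following the schedule puts 89% of covered days inside two forms (88% if forms are answered at week start). Following the biweekly text on time puts none there. Second, under either frequency no event form is scheduled after Week 9. With 12 weeks of participation and forms answered on time, at least 21 of 84 days (25%) rely on spontaneous reports, or 28 days (33%) if the last biweekly form is at Week 8. With an 8-week end and a Week 9 form, only the serious-event window is left uncovered.

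These are shares of days, not of events, and they rest on an assumed answering day. The matter is modest because safety is descriptive and no efficacy inference is touched. It is worth correcting because the correction is nearly free.

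**What to change.** 1. Settle one frequency, so that section 1.3 agrees with sections 8.3.3.1 and 8.3.4.
2. Word the recall as since your last event form, or since starting the programme for the first one. This is preferable to only matching a fixed look-back to the sending interval, because section 6.4 allows late and same-day completion.
3. Add the Events Assessment to the existing Week 12 survey, with recall since the previous form.
4. State in section 9.4.4 that events are summarised by the onset date collected at the call, with repeat reports of one episode counted once.
5. Reconcile the synopsis and sections 1.3, 4.4, 5.5 and 6.1.2 on the end of participation, continued use and headset return, and section 8.3.4 with the schedule on the Day 1 event review.

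The cost is a changed question stem, one or two extra items in surveys already sent, a schedule edit, and a few more follow-up calls.
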